3.1.2. Endpoints

Primary Endpoint:

Patient Reported Quality of life related to Radiation Induced Nausea and Vomiting (RINV) as scored by the Functional Living Index – Emesis (FLIE) at day 5 post RT start.

Secondary Endpoints

Primary efficacy outcome

- Control of RINV measured by a daily patient diary (day 1-5)

Secondary Patient Reported Outcome Measures (PROMs)

- Pain flare measured by the Brief Pain Inventory (BPI)
- Diary of medication use (specifically anti-emetics)
- PRO-CTCAE T11 – L5 & Pelvis:
 - Decreased appetite
 - Nausea
 - Vomiting
 - Diarrhea
 - Radiation skin reaction
 - Pain flare
 - Fatigue
- Pain response assessed by the Brief Pain Inventory.
- Proportion of patients who receive treatment within 1 day, 2 days, 3 days, 4 days, 5 days, or more than 5 days,
- Toxicity assessed at baseline and follow-up
- Quality of Life: single item from EORTC QLQ C-15 PAL: How would you rate your overall quality of life during the past week
- Performance status: as reported by patient with PRO-ECOG
- Cost effectiveness of SUPR vs. VMAT assessed by EQ-5D-5L

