5.3.2. Permitted Concomitant Therapy

Nausea prophylaxis

Dexamethasone may be given for nausea prevention, though is not mandated.

Analgesics

Analgesics are allowed to be prescribed as needed by the patient to obtain optimal pain control.

Concurrent hormonal therapy

Concurrent receipt of hormonal therapy is allowed during this study.

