5.5. Subject Compliance/Deviations

Subject compliance, such as attending study visits and completing questionnaires, will be monitored via REDCap. If any visits are not completed, investigator or delegate must call and conduct follow-up over the telephone. Missed visits must be documented in the deviation log.

Deviations to eliminate immediate hazards to study subjects must be reported to the Study PI immediately upon discovery and to the REB within 7 calendar days. All other reportable deviations must be reported to the Study PI immediately, however to the REB within 15 calendar days. See section **12.1.2 Protocol Deviations** for a list of deviations.

Protocol number v12.0; 16 Apr 2024

6. Dose Modifications

N/A.

7. Assessment of Efficacy

Treatment Response Evaluation

FLIE:

Scores on all individual questions will be weighted equally, reversed if required and summed to create an overall FLIE score. Minimum score and maximum score will be 18 and 126 respectively. A low score is favorable, reflecting less nausea and vomiting.

The paper version of the FLIE is a 7-point Likert-scale. Patients' responses will be rounded to the closest point on the scale for entry in the digital database. I.e. if the response is 1.4, this will be rounded to 1. If the response is 1.5, it will be rounded to 2.

RINV:

Complete control: no increased episodes of nausea or vomiting with no increased use of anti-emetic medication from baseline

Partial control: 1-2 increased episodes of nausea or vomiting with no increased use of anti-emetic medication compared to baseline

Uncontrolled response: 3 or more increased episodes of nausea or vomiting, or increased use of anti-emetic medication from baseline

Overall control: includes complete and partial control

Pain:

Complete response: pain score of 0 at treated site with no increase in analgesic intake (stable or reducing analgesics in daily oral morphine equivalent (OMED).

Partial response: pain reduction of 2 or more at the treated site on a scale of 0 to 10 without analgesic increase, or analgesic reduction of 25% or more from baseline without an increase in pain.

Pain progression: Increase in pain score of 2 or more above baseline at the treated site with stable OMED, or an increase of 25% or more in OMED compared with baseline with the pain score stable or 1 point above baseline.

Indeterminate response: Any response that is not captured by the complete response, partial response or pain progression definitions¹⁴.

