9.1. Statistical Methods

Patients will be analyzed in the groups to which they are assigned (intention-to-treat). All analyses will be done using t-tests between the average scores of the two arms.

RINV will be assessed via Functional Living Index – Emesis (FLIE) scores compared between the two arms at baseline and day 5 post start of RT

Health-Related Quality of Life (HRQoL) will be measured using the EQ-5D-5L and combined with survival outcomes to explore differences in Quality Adjusted Life Year (QALY) gains or losses between treatments

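### Pain response combines pain score with analgesic use, but the only stated analysis is a t-test of average scores with no interval, which neither analyses that endpoint nor can support the hypothesis of no difference

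*Combined protocol and SAP*

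**What the plan says.** Section 3.1.2 lists the endpoint as "Pain response assessed by the Brief Pain Inventory", without naming a visit, an item or a site. Sections 2.1 and 3.1.1 hypothesise that it will not differ between arms, because the dose is the same.

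Section 7 defines it by category:

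- Complete response: "Complete response: pain score of 0 at treated site with no increase in analgesic intake".
- Partial response: a fall of at least 2 points without more analgesic, or "analgesic reduction of 25% or more from baseline without an increase in pain".
- Progression has two limbs. The first works on the pain score: "Increase in pain score of 2 or more above baseline at the treated site with stable OMED".
- The second limb of progression works on analgesic use: "an increase of 25% or more in OMED compared with baseline with the pain score stable or 1 point above baseline".
- Everything else: "Indeterminate response: Any response that is not captured by the complete response, partial response or pain progression definitions".

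On analgesics, section 5.3.2 says: "Analgesics are allowed to be prescribed as needed by the patient to obtain optimal pain control".

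The method in section 9.1 is a single sentence covering every endpoint: "All analyses will be done using t-tests between the average scores of the two arms". Neither section 9.1 nor section 9.2 mentions a confidence interval, an equivalence margin, or a rate or power for pain response. The one calculation on proportions, in section 9.2, concerns RINV.

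**The concern.** The endpoint is a category built from two measurements, while the stated analysis is a comparison of means of one. A t-test of mean pain scores is a legitimate analysis, but of a different quantity. Analgesics are taken as needed, so two arms can have equal mean pain while one uses more drug to get there. The section 7 categories would show this; the means would not.

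The hypothesis makes this matter more. Moving patients to VMAT is easier to justify if pain relief is not lost, and a non-significant t-test could easily be taken as showing that. Without an interval, the reader cannot see how large a loss remains possible.

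The quantity itself is also open. Section 4.8 schedules the Brief Pain Inventory (BPI) at baseline, on Day 1 (unless it was collected within 7 days of first treatment), and at weeks 2 and 4 after the last RT. Section 3.2 allows up to three fields, and lesions outside T11–L5 and the pelvis may be treated with a technique chosen at discretion. Section 7 refers only to the treated site. Visit, baseline and site could therefore all be chosen after the data are seen.

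**Working it through.** **1. The plan's own figure.** Inputs from section 9.2: FLIE means 36 and 28, SD 16, alpha 0.05 (two-sided assumed), power 0.90, dropout 30%.

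n per arm = 2 × (1.960 + 1.282)² × 16² / 8² = 84.1, rounded up to 85. Total 170 / 0.70 = 243. A t-based calculation gives 86 per arm and 246. The stated 250 is reproduced, and no pain quantity enters it.

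**2. Score against category.** Applying the section 7 rules:

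| Baseline pain | Follow-up pain | OMED change | Category |
|---|---|---|---|
| 4 | 4 | −25% | Partial response |
| 4 | 4 | 0 | Indeterminate |
| 4 | 4 | +25% | Progression |
| 4 | 5 | +25% | Progression |
| 4 | 6 | 0 | Progression |
| 4 | 6 | +25% | Indeterminate |
| 4 | 7 | +50% | Indeterminate |
| 0 | 0 | 0 | Complete response |

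Rows 1–3 have the same pain score and three different categories, so a mean score cannot stand in for the category. Rows 4–7 show that the progression rule is not monotone. Pain up 1 with OMED up 25% is progression, but pain up 2 or more with OMED up 25% or more meets neither limb, whatever meaning is given to stable OMED. Such a patient cannot be a complete or partial responder, so the combined response rate is unaffected.

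**3. Width of the interval.** The documents give no pain response rate, so p = 40–70% is assumed in both arms. Half-width = 1.96 × √(2p(1−p)/n), with n per arm.

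| Evaluable | n per arm | p = 0.4 | 0.5 | 0.6 | 0.7 |
|---|---|---|---|---|---|
| 250 × 0.70 = 175 | 87.5 | 14.5 | 14.8 | 14.5 | 13.6 |
| 250 × 0.80 = 200 | 100 | 13.6 | 13.9 | 13.6 | 12.7 |
| 250, no loss | 125 | 12.1 | 12.4 | 12.1 | 11.4 |

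(Half-widths in percentage points.) Section 9.2 states the 30% and 20% dropout rates for FLIE and RINV, which are measured by day 5. No rate is given for weeks 2 or 4. If loss is heavier there, the interval is wider than the first row.

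A half-width of 10 points would need n = 2p(1−p) × (1.96/0.10)², about 161–192 evaluable per arm.

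**4. What a non-significant result would mean.** Two-sided 5% test of two proportions, with assumed true rates:

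| True response | Power, 175 evaluable | Power, 200 evaluable | Non-significant |
|---|---|---|---|
| 60% vs 50% | 0.264 | 0.294 | 74% or 71% |
| 60% vs 45% | 0.511 | 0.566 | 49% or 43% |

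**5. Patients with no pain at baseline.** No criterion in section 4.1 requires pain, and complete response has no baseline condition, so the last row of the first table can occur. If a share f of patients is like this and responds equally in both arms, a difference shrinks to (1−f) times its size. A 15-point difference becomes 14.3 at f = 5%, 13.5 at 10% and 12.0 at 20%. The value of f is unknown and may be near zero, since section 2.1 describes mainly painful metastases.

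**The case against.** The strongest reply is that section 9.1 is loose shorthand. Section 7 takes care to build OMED into the categories, and section 9.2 treats RINV as a proportion, so the authors may intend a t-test on a 0/1 response, which would give nearly the same answer as a test of proportions. That is plausible, and a reader might wrongly infer that the plan means to disregard analgesic use. The documents do not show such an intention. They show only that the one stated method, taken as written, leaves analgesics out, and that no other reading is spelled out.

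A reader might also infer that the trial will claim equivalence in pain relief, or needs a margin and more patients. That is not supported either. The hypothesis is an expectation on a secondary outcome, no equivalence test is planned, and no passage says a non-significant result will be taken as proof. What stands is that the plan does not rule this out and specifies no interval that would guard against it. A margin would be needed only if equivalence were to be claimed.

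Finally, the progression gap touches no endpoint listed in section 3.1.2, the definitions cite a consensus not available here, and pain-free patients may be very few. These are fair reasons to treat both as minor and to keep the as-written versions.

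**Conclusion.** As written, section 9.1 does not analyse the pain response that section 7 defines, and its result could not support no difference. Under the assumed response rates, an observed difference of zero would still leave a loss of about 14–15 points possible with 175 evaluable patients, 13–14 with 200, and 11–12 even with no loss to follow-up. The widths rest on assumed rates and, for the first two, on dropout borrowed from other endpoints. The mismatch between definition and method rests on the text alone.

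This should be corrected, but it does not threaten the primary FLIE comparison. The progression rule misclassifies patients who worsen on both measures, which is a minor fault. The absence of a baseline-pain condition warrants reporting, not a change to the main analysis.

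**What to change.** **Main change, section 9.1.**

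- Analyse pain response as the between-arm difference in the proportion with complete or partial response, adjusted for the dose stratum (8 Gy/1 vs 20 Gy/5), with its 95% confidence interval.
- Name one visit (week 2 or week 4), one BPI item, and one index site treated with the randomized technique.
- Name the pain baseline: the pre-randomization BPI, or Day 1 where repeated.
- Name the OMED baseline and time window.
- State that no difference will not be concluded from a non-significant test.

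**Check first.** Section 5.3.5 describes a cumulative medication form and section 4.8 a baseline and follow-up form, but neither says that analgesic dose or as-needed intake is recorded at the chosen visit. The diary is aimed at anti-emetics. No section shows a separate pain score for each field. If the forms lack these items, the change is more than wording.

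**Minor change, section 7.** Let the progression outcome category also capture pain up 2 or more with OMED increased, and report the as-written categories in parallel.

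**Pain-free at baseline.** Keep all patients in the main analysis, so that those whose analgesic use falls still count. Report the number with baseline pain 0 by arm, and give an analysis restricted to baseline pain above 0 only as a sensitivity analysis.

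**Cost.** A few sentences, a form check and a little more analysis, best settled before database lock (section 3.3). The sample size was set for FLIE and stays as it is, so the pain comparison may have to be reported as inconclusive.

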2.3. Study Population

Patients with a clinical diagnosis of bone metastases, meeting all inclusion and exclusion eligibility criteria.

3. Trial Design

This is a randomized, multi-centre, pragmatic phase III study in palliative patients with bone metastases. Randomization will be performed on patient-level, meaning that if a patient is treated for multiple bone metastases in the same course, all will receive the same treatment technique. This applies only to bone lesions, as per section 3.2. Any additional lesions to be treated will be at the RO's discretion.

Patients will be stratified by treatment dose of either 8 Gy in a single fraction or 20 Gy in 5 fractions.

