3.1. Study Objectives and Endpoints

3.1.1. Objectives

Primary Objective

The primary objective is to compare patient-reported Quality of Life related to Radiation Induced Nausea and Vomiting (RINV) between standard palliative radiotherapy and VMAT.

Secondary Objective(s)

To assess rate of complete control of RINV, compare patient reported toxicity, and evaluate pain response. However, we hypothesize that there will be no difference in pain response between the two arms, because they are receiving the same dose.

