3.2. Entry Procedures

PRE-TREATMENT ASSESSMENT

- ECOG status
- Eligibility according to inclusion and exclusion criteria
- Patient Reported Outcomes
 - Brief Pain Inventory
 - Functional Living Index – Emesis
 - EQ-5D-5L

Entry Procedures

All randomizations will be done using a computer-generated randomization scheme.

All eligible patients enrolled in the study by the participating treatment centre will be assigned a study number, which must be used on all documentation.

The following information will be required:

- Trial code (where applicable)
- Name of investigator under whose name the patient will be randomized
- Informed consent, version date, date signed by patient, name of person conducting consent discussion and date signed by the person who conducted the consent from discussion
- Confirmation that the patient meets the eligibility requirements in Section 4.0 (as per completed Subject Registration Form)

Stratification factors

All metastases lying at least partly within T11-L5 or the pelvis will be treated according to randomization technique, and should receive the same dose (either 8 Gy in 1 fraction or 20 Gy in 5 fractions), chosen pre-randomization. All other bone metastases that need to be treated can be treated with either 20 Gy in 5 fractions or 8 Gy in 1 fraction, can be treated at the same time. Technique for these lesions can be chosen by RO or centre discretion. The total number of fields that can be treated synchronously is 3, and included both eligible and ineligible fields. If additional bone metastases are symptomatic, they can be treated at a later time, no sooner than 4 weeks from the end of radiotherapy on trial.

A description of the measures taken to minimize avoid bias including:

a. Randomization (simple/restricted/blocked/stratified)

Simple randomization with stratification will be used to randomly assign patients to either Arm 1 or Arm 2 in a 1:1 ratio using a computer-generated randomization scheme known only to the trial statistician.

b. Blinded/Unblinded

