4.1. Inclusion Criteria

Subjects must meet all of the following criteria to be eligible for participation in this study:

- Age 18 or older
- Able to provide informed consent
- Clinical diagnosis of cancer with bone metastases (biopsy not required)
- Currently being managed with palliative intent RT to 1-3 RT fields for bone metastases, at least one RT field (PTV) must (at least) partly lie within T11-L5 or pelvis.
- ECOG Performance Status 0-3
- Patient has been determined to potentially benefit from 8 Gy or 20 Gy
- Radiation Oncologist is comfortable prescribing 8 Gy in 1 fraction or 20 Gy in 5 fractions RT for bone metastases
- Negative pregnancy test result for women of child-bearing potential
- The baseline assessment must be completed within required timelines, prior to randomization.
- Patients must be accessible for treatment and follow-up. Investigators must assure themselves the patients randomized on this trial will be available for complete documentation of the treatment, adverse events, and follow-up.
- For simplicity of planning, expected GTV should be less than 20 cm based on radiological or clinical evidence
- Patient must be prescribed a 5-HT3 receptor antagonist (e.g. Ondansetron) as antiemetic prophylaxis prior to RT start.
- Patient is able and willing to complete the quality of life questionnaires, and other assessments that are a part of this study, via paper or using REDCap if they provide their email address on the informed consent

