4.8 Schedule of Assessments

Assessment	Screening: Visit-1	Baseline, Enrollment, Randomization: Visit 1	Treatment: Visit 2 (Day 1)	Treatment / Follow-Up (for 8Gy/1# patients) Visit 3 (Day 5)	Follow-Up Visit 4 (W2 post last RT) +/- 3 days	Follow-Up Final Visit (W4 post last RT) +/- 3 days
Informed Consent	X					
Inclusion/Exclusion Criteria	X					
Enrollment/ Randomization		X				
*Medical History/ Comorbidities	X					
Physical Examination	X					
€Pregnancy Test	X					
Patient Diary (provided to patient)			X	X		
**Brief Pain Inventory		X	X		X	X
**Functional Living Index - Emesis		X	X	X	X	X
PROMS		X	X		X	X
Treatment Related Data			X			
***Baseline & Follow-up		X	X		X	X
EQ-5D-5L		X			X	X

*may be done within 90 days, or 3 months, prior to enrollment

**BPI, FLIE and PROMS on Day 1 does not need to be repeated if collection was done within 7 days of first treatment (day 1).

***Baseline & Follow-up form does not need to be repeated if collection was done within 2 days of first treatment (day 1). If RT starts 3 or more days after baseline collection, or anytime medication changes (if known), this form will need to be repeated

€Urinalysis or serology – per institutional guidelines.

Protocol number v12.0; 16 Apr 2024

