5.2.1.4. PROMS Questionnaire

Patient reported, combined questionnaire including:

- Single item from EORTC QLQ C-15 PAL (How would you rate your overall quality of life during the past week?) to assess overall quality of life
- PRO-CTCAE to assess fatigue and skin burn
- PRO-ECOG to assess functional status

Electronic or Paper both available.

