5.2.1.6 Baseline Symptoms and Post-Treatment Toxicity

Baseline Symptoms and Post-Treatment Toxicity assessed by care provider at baseline and follow-up.

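### The planned unadjusted t-test of secondary toxicity scores is valid, but gives up precision that the pre-randomisation score and dose stratum could supply

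*Combined protocol and SAP*

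**What the plan says.** Section 9.1 (Statistical Methods) states: "All analyses will be done using t-tests between the average scores of the two arms". No section names a covariate or brings the stratification factor into an analysis.

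Toxicity is among the secondary objectives in 3.1.1: "To assess rate of complete control of RINV, compare patient reported toxicity, and evaluate pain response". The data that bear on it are these:

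- **Schedule (4.8).** The PROMS questionnaire and the Baseline & Follow-up form are due at Visit 1, Day 1, and weeks 2 and 4 after the last RT.
- **Timing of baseline (4.1).** "The baseline assessment must be completed within required timelines, prior to randomization".
- **Day 1 repeats (4.8).** "BPI, FLIE and PROMS on Day 1 does not need to be repeated if collection was done within 7 days of first treatment". The Baseline & Follow-up form has its own rule: it is repeated if RT starts three or more days after baseline collection, or if medication is known to have changed.
- **Care-provider form (5.2.1.6).** "Baseline Symptoms and Post-Treatment Toxicity assessed by care provider at baseline and follow-up". Its scale is not shown.
- **Items collected.** Section 3.1.2 lists seven PRO-CTCAE items and the Protocol Summary mentions fatigue, nausea and vomiting. Section 5.2.1.4 says only "PRO-CTCAE to assess fatigue and skin burn". Fatigue is the one symptom common to all three.
- **Stratum.** Section 3 (Trial Design): "Patients will be stratified by treatment dose of either 8 Gy in a single fraction or 20 Gy in 5 fractions". Section 3.2 adds: "Simple randomization with stratification will be used to randomly assign patients to either Arm 1 or Arm 2 in a 1:1 ratio".

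**The concern.** Patients with bone metastases may report symptoms such as fatigue before any radiation. Their score two or four weeks later then partly reflects where they started. A t-test of follow-up means leaves that between-patient variation in the error term. A model with the baseline score removes it, and adding the stratum respects the way patients were randomised.

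What is at stake is the width of the interval for the SUPR versus VMAT difference in toxicity. Section 2.1 makes lower toxicity with VMAT the trial's hypothesis, so a sharper estimate has value. The size of the t-test and the planned 250 patients are not in question.

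**Working it through.** **1. Patients available.** The plan gives no sample size, SD or effect for toxicity, so its FLIE calculation in 9.2 supplies the number of patients. With means 36 and 28, SD 16, power 0.9 and two-sided alpha 0.05 (sidedness is not stated, but one-sided gives only 198):

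n per arm = 2 × (1.960 + 1.282)² × (16/8)² = 84.1, so 85 per arm and 170 in total. Dividing by 0.7 for 30% dropout gives 243; the exact t-test gives 86 per arm and 172/0.7 = 246. The stated 250 is reproduced within 3%.

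After 30% dropout, 250 × 0.7 = 175 remain, taken as 87 per arm. Using this dropout at weeks 2 and 4 is an assumption.

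**2. Reference effect.** In SD units, SE of the t-test = √(2/87) = 0.1516. With 172 degrees of freedom, 80% power corresponds to a difference of 0.427 SD. This is a yardstick, not an effect the plan expects.

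**3. Adjusted analysis.** Let r be the assumed correlation of follow-up with baseline.

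- Interval width relative to the t-test: √(1 − r²)
- Equivalent evaluable patients: 174/(1 − r²)
- Power: noncentral t with 170 df and residual variance (1 − r²)(1 + 1/169)

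| Assumed r | Interval narrower by | Equivalent patients | Power |
|---|---|---|---|
| 0 | 0% | 174 | 79.8% |
| 0.3 | 4.6% | 191 | 83.3% |
| 0.5 | 13.4% | 232 | 89.7% |
| 0.7 | 28.6% | 341 | 97.4% |

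The factor 1 + 1/169 costs about 0.3% in width. At r = 0 power is 0.2 points below the t-test's 80%.

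**4. Stratum alone.** With 20 to 50% of patients on 20 Gy and strata differing by 0 to 0.5 SD (both assumed), power rises to 82.3% at most. Nearly all the gain comes from the baseline score.

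**5. Skewed scores.** Simulation of a 0–4 score with 40/25/20/10/5% at each level (20,000 trials per setting):

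| Observed r | t-test power | Adjusted power |
|---|---|---|
| 0 | 80.0% | 79.9% |
| 0.26 | 80.3% | 82.9% |
| 0.44 | 79.9% | 87.8% |
| 0.63 | 80.1% | 95.0% |

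For an item scored zero by 96% of patients at baseline, power went from 81.0% to 80.9% in one setting and from 82.3% to 82.6% in another: no real gain. Rejection under the null was 0.047 to 0.052 throughout.

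**6. Which baseline.** Suppose the Day 1 score differs between arms by a shift s while follow-up does not differ. Adjusting for Day 1 then biases the contrast by r × s. At r = 0.5 and s = 0.1, 0.2 and 0.3 SD the bias is 0.05, 0.10 and 0.15 SD, against an SE of 0.1516 × 0.866 = 0.131. Simulated false-positive rates were 6.5, 11 and 20%; the t-test stays at 5%. The documents give no size for s. A score completed before randomisation has an expected s of zero.

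**The case against.** **The plan contains no error here.** The t-test is unbiased under 1:1 randomisation, and the plan does not power the toxicity comparisons. This stands. A reader might infer that ignoring baseline or stratum invalidates the analysis; the documents do not support that, and the only loss is precision.

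**The gain is not free or general.** Every correlation above is assumed. Section 5.2.1.4 confirms two PRO-CTCAE items, and one of them, skin reaction, is the kind that gains nothing. The care-provider scale is not shown, so a linear model suits it only if it is numeric. This stands and limits the benefit mainly to fatigue.

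**The latest pre-treatment score looks like the better covariate.** That inference should be resisted. A Day 1 form can follow randomisation, the trial is open-label (3.2), and VMAT patients are expected to wait longer (2.1), so the presence and content of Day 1 forms could differ by arm. Step 6 shows the possible harm.

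**The same sentence governs FLIE.** True, and adjustment would help there too. But a change for FLIE would not by itself give the toxicity scores a model.

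**The scores are ordinal.** An ordinal model is a reasonable alternative. The linear model keeps the mean difference that the plan already compares, and it held its size in the simulation.

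**Average scores might mean average changes.** Section 9.1 does not say so. Under that reading the t-test would have 51, 66, 80 and 95% power at r = 0, 0.3, 0.5 and 0.7, below the follow-up comparison whenever r is under 0.5.

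**Conclusion.** The point holds as an optional efficiency improvement. Section 9.1 leaves unused a baseline score taken before randomisation and the stratification factor. Using them would narrow the interval by about 0, 5, 13 and 29% at assumed r = 0, 0.3, 0.5 and 0.7. The percentage narrowing depends on r, apart from the small cost of estimating two covariates. The power and patient-equivalent figures also assume 87 evaluable patients per arm, and the power figures a 0.427 SD effect.

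The benefit is likely to be useful for fatigue and about nil for symptoms that are rare at baseline. The method is well established; how much it would gain in this trial cannot be known from the documents. Type I error is protected only if the covariate is the score completed before randomisation.

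**What to change.** Add to 9.1:

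*Each secondary toxicity score with a baseline (PRO-CTCAE items actually collected and, if numerically scored, care-provider symptom scores) will be compared at W2 and at W4 by a linear model with arm, the Visit 1 score completed before randomisation, and the 8 Gy/20 Gy stratum. Day 1 scores will not be used as the baseline covariate. Adjusted mean differences with 95% CIs will be reported as secondary.*

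No new visits, forms or patients are needed. The statistical cost is two degrees of freedom, about 0.2 power points at r = 0. The administrative cost is a wording change to a protocol already at v12.0, with ethics board review and Study PI pre-approval for sites (12.1.1). It should be settled before any comparison of the arms; 3.3 schedules an interim analysis from 1 December 2024 and database lock from 30 August 2025. If no amendment is made, 9.3 allows a departure from the statistical plan to be described and justified in the report, though a choice made before the arms are compared carries more weight.
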